### ***10.1.1.3 Sensitivity and Subgroup Analyses***

The primary efficacy analysis of time to adjudicated clinical worsening events will also be provided for the Per-protocol Population.

The following sensitivity analyses will be performed:

- For all subjects who drop out from the study early, they are considered as having a clinical worsening event. Time to event will be calculated from randomization to subject's discontinuation date.
- For all subjects who drop out from the study early due to AEs, they are considered as having a clinical worsening event. Time to event is calculated from randomization to subject's study discontinuation date.

The time from randomization to clinical worsening will also be compared between treatment groups using a Cox proportional-hazards regression model, adjusting for Baseline 6MWD category ( $\leq 350$  meters versus  $> 350$  meters) and background PAH therapy (as a categorical variable: PDE5-I/sGC stimulator or ERA). Hazard ratio and its 95% confidence interval will be calculated. SAS Procedure PHREG will be used and the pseudo SAS statements are listed below:

```
proc phreg;
  Model TimeToWorsening*Censor_Status(1) = treatment;
  Strata BGTX B_6MWD / risklimits ties=efron;
run;
```

where BGTX variable denotes the background therapy and B\_6MWD denotes the Baseline 6MWD category  $\leq 350$  meters versus  $> 350$ .

Subgroup analyses will be performed on the following factors: background PAH therapy, PAH etiology, Baseline WHO FC, age group (<65 years versus  $\geq 65$  years), Baseline 6MWD category, sex (male versus female), maximum dose achieved (<9 mg versus  $\geq 9$ mg total daily dose), and geographic region as specified in Section 8.2. The estimated hazard ratio between the active and placebo groups from this model will be calculated and displayed along with its 95% confidence interval on the summary and analysis table and plot.

Since clinical worsening is a composite endpoint, the following components of this composite endpoint will also be summarized and analyzed with the same approach as the composite endpoint:

- Time to death (all causes) during the study
- Time to hospitalization due to worsening PAH

In addition, time to death (all causes) by the end of the study will also be summarized and analyzed. For time to death by the end of the study analysis, the vital status for all subjects will also be collected throughout the study to the completion of the last subject in the study including subjects who discontinued the study early and subjects who rolled over to the extension study (TDE-PH-311).

For each of the above time-to-event variables, the assumption of proportional hazards will be assessed using a log-log survival plot, with log of time as the x-axis and log negative log survival distribution function (SDF) as the y-axis. This plot will be reviewed to assess if the curves were parallel and thus the proportional hazards assumption for treatment is met. In addition, the proportional hazards assumptions will also be checked by using the time \* treatment or time\*covariate interactions in the model. The PROC LIFETEST procedure in SAS will be used to calculate the survival function estimates for the plots. If the non-proportional hazard model is suggested, the alternative approaches, such as an extension of the Cox regression model, may be explored.

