7.4 STUDY DRUG TERMINATION VISIT

Subjects will continue in the study until they experience clinical worsening, prematurely discontinue the study for any reason, or approximately 205 adjudicated clinical worsening events have occurred. If a subject remains ongoing with study treatment at the time when approximately 205 adjudicated clinical worsening events have occurred, the Study Drug Termination Visit should be scheduled as soon as possible. The following assessments will be conducted immediately after the decision is made to discontinue study drug (prior to down titration).

- Vital signs (following at least 5 minutes of rest)
- Physical examination
- Clinical worsening assessment
- WHO Functional Class for PAH
- AE assessment
- Drug accountability/compliance
- 12-lead ECG (following at least 5 minutes rest in the semi-recumbent position)
- Concomitant medications
- 6MWT/Borg dyspnea score (6MWT to be initiated 3 to 6 hours after last dose of study drug and following at least 5 minutes of rest; Borg dyspnea score to be conducted immediately following 6MWT)
- Urine pregnancy test (for WOCBP)
- Clinical laboratory tests/NT-proBNP

- Collection of blood sample for evaluation of blood biomarkers (optional)
- Collection of urine sample for evaluation of urine biomarkers (optional)
- Collection of blood sample for evaluation of pharmacogenomics (optional)

If the subject permanently discontinues study drug prior to Week 24 for any reason other than clinical worsening (e.g., AEs, addition of second PAH-approved oral therapy), the subject should immediately complete the study drug termination visit assessments and be encouraged to remain in the study and complete all visits up to and including Week 24. The Study Drug Termination Visit assessments should be conducted immediately after the decision is made to discontinue study drug (prior to down titration).

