10.2 SAMPLE SIZE

Approximately 205 adjudicated events will provide at least 90% power with a Type I error rate of 0.05 (two-sided hypothesis) to detect a difference in the time to clinical worsening between treatment groups, assuming exponential distributions and an underlying hazard ratio of 0.62. Assuming a placebo median event time of 32 months (which corresponds to an event rate of 23% at Month 12), this hazard ratio corresponds to a median time to event of 51 months for the UT-15C group, or an event rate of 15% at Month 12. If accrual of subjects is completed during the first three years and 10% of the subjects drop out by the end of the study, a total sample size of at least 610 subjects with a maximum of 850 subjects is expected to generate approximately 205 adjudicated events over the course of the study.

Based on the results of other PAH studies, (e.g., AMBITION [ambrisentan and tadalafil] and GRIPHON [selexipag]; Galiè, 2015; Sitbon, 2015) an interim analysis for efficacy is planned when 75% of the total adjudicated worsening events have occurred. In order to control the total alpha at a two-sided 0.05 level, the method of Lan and DeMets with O'Brien-Fleming-type alpha spending function will be used to calculate the boundaries for stopping the study for efficacy at the interim analysis [Lan and DeMets, 1983]. If the interim analysis is performed with 154 events, the boundary on the p-value scale will be 0.020 and 0.044 for the final analysis. Calculations will be performed in EAST version 6.4, Cytel Inc, using simulated power.

If enrollment continues beyond the interim efficacy analysis, final enrollment will be stopped when approximately 190 clinical worsening (morbidity or mortality) events have been reported by Investigators and reviewed by the Medical Monitor. Subjects will be followed until the occurrence of approximately 205 adjudicated clinical worsening events, at which time all remaining subjects will be transitioned to the open-label extension study. No more than 850 subjects will be enrolled.

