### 9.1 SUBJECT ACCOUNTABILITY

All subjects' disposition information will be listed, including the study population the subjects belong to, whether or not subjects completed the study drug treatment, reason study drug was stopped, whether or not subjects completed at least 24 weeks of study assessments, primary reason for not completing 24 weeks of assessments, whether or not subjects completed the study, reason for not completing the study, and whether or not subjects rolled over to the open-label extension study (TDE-PH-311).

The listing of subject accountability will include dates of informed consent, randomization, first study drug dose, last study drug dose, last dose week, and last assessment week.

Whether subjects received study drug; whether subjects completed the Weeks 4, 8, 12, and 24 assessments, and every 12-week follow-up assessment thereafter; study drug termination status; and study discontinuation status will be summarized by treatment group and overall.

Information regarding whether each subject is included in each analysis population (see Section 6) will be listed. If a subject is not included in a particular analysis population, the reason for exclusion will be noted on the listing. Also noted on the listing will be the

randomized treatment assignment and the actual treatment subjects have received. The summary will include the frequency and percentage of all subjects in each analysis population by treatment group and overall.

All stratification information used in the random assignment of subjects to treatment group (from the central randomization database) will be listed, including date and time of randomization, background PAH therapy, Baseline walk distance category, whether or not the treatment is unblinded, and if so, date/time of blind break. For observations where any stratification information has been corrected, both the original and corrected information will be listed. Background PAH therapy and Baseline walk distance used for randomization stratification will be summarized by treatment group and compared using Fisher's exact test or Wilcoxon rank sum test, as appropriate.

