#### ***10.1.1.2 Primary Efficacy Analyses***

Data on the Clinical Worsening Assessment page of the eCRF will be used in determining clinical worsening status. Investigator-reported clinical worsening events will be reported directly from the eCRF data, regardless of the outcome of the adjudication committee review. An independent adjudication committee will be utilized to adjudicate all investigator-reported clinical worsening events. Adjudicated clinical worsening events will be reported using data received from the adjudication committee.

Subjects who discontinue study drug for reasons other than clinical worsening will be censored at the time of discontinuation of the study drug. Non-fatal clinical worsening events that occur more than 7 days after permanent study drug discontinuation will not be included in the summary and analysis of clinical worsening events. However, all deaths within the study follow-up period (30 days after the last study drug dose) will be included as clinical worsening events. Time to clinical worsening will be summarized by treatment group using product-limit estimates calculated by the Kaplan-Meier method, and displayed graphically as Kaplan-Meier curves. A tabular summary of this analysis will include the number of subjects at risk (sample size), estimated median duration, and a 95% confidence interval for the median duration for each treatment group.

For the primary efficacy analysis of time to adjudicated clinical worsening, the log-rank test adjusted for the type of background therapy (PDE5-I or sGC stimulator versus ERA) and the Baseline 6MWD ( $\leq 350$  meters versus  $> 350$  meters) will be used to calculate the p-value for treatment differences in the ITT Population.

The SAS Procedure LIFETEST will be used. The pseudo SAS statements are listed below:

```
proc lifetest;
  time TimeToWorsening*Censor_Status(1);
  strata BGTX B_6MWD / group=Treatment test=all;
run;
```

where BGTX variable denotes the background therapy and B\_6MWD denotes the Baseline 6MWD category ( $\leq 350$  meters versus  $> 350$  meters).

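### The AE drop-out sensitivity analysis is keyed to leaving the study, the primary censoring to stopping study drug, so subjects censored for an AE drug stop can be missed

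*SAP*

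**What the plan says.** **Primary rule (SAP 10.1.1.2).** "Subjects who discontinue study drug for reasons other than clinical worsening will be censored at the time of discontinuation of the study drug". Non-fatal worsening more than 7 days after permanent drug stop is left out.

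**Sensitivity analyses (SAP 10.1.1.3).** One counts every early study drop-out as an event. The other is limited to AEs: "For all subjects who drop out from the study early due to AEs, they are considered as having a clinical worsening event". The AE version is dated at study discontinuation. The all-cause version gives only a discontinuation date, without saying whether of drug or study. SAP 8.3.1 lists the same pair as a check on missing data and calls them early termination, again without saying of what.

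**Drug stop and study exit are separate states.** Under Protocol 7.4, a subject who stops drug before Week 24 for a reason other than clinical worsening (AEs are named) completes the termination assessments and should "be encouraged to remain in the study and complete all visits up to and including Week 24". Table 3-1 footnote m and Protocol 4.3.1 say much the same. SAP 9.1 lists the reason study drug was stopped and, as a different item, the "reason for not completing the study".

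**The concern.** The AE analysis is there to challenge censoring that may be informative and unequal between arms. To do so it must convert the subjects whom the primary rule censored for an AE. It selects them by a different act (leaving the study), a different recorded reason and a different date.

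Take a subject who stops drug for an AE at Week 6 and attends to Week 24. The primary analysis censors at about Week 6 because of the AE. The later study exit may carry another reason. Read literally, the AE analysis then leaves this subject censored. If AE drug stops are commoner on UT-15C, the omitted subjects are mainly UT-15C subjects and the check looks more reassuring than intended. If such a subject has a non-fatal worsening more than 7 days after drug stop, the primary analysis excludes that known event, and the AE analysis need not pick it up either.

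**Working it through.** **1. The plan's own figure.** Inputs from Protocol 10.2: 205 events, two-sided alpha 0.05, "assuming exponential distributions and an underlying hazard ratio of 0.62", placebo median 32 months. Schoenfeld power = Φ(√205/2 × |ln 0.62| − 1.960) = Φ(7.159 × 0.478 − 1.960) = Φ(1.462) = 92.8%. At the final-look alpha of 0.044 it is Φ(3.422 − 2.014) = 92.0%. Freedman's formula gives 91.9% and 91.1%; the two-look design gives 92.4%. The stated power of at least 90% reproduces. The 12-month rates are 1 − exp(−12 ln 2/32) = 22.9% for placebo and, with the hazard multiplied by 0.62, 14.9% for UT-15C (stated 23% and 15%). With 610 subjects, 36-month accrual and 10% drop-out, 217 to 233 events are expected by month 48. None of this is in dispute; it sets the frame for the illustration.

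**2. How many subjects could be affected.** The documents give no AE drug-stop rate for this trial. As an assumption, take TDE-PH-301 (Protocol 1.2.4): 14% on UT-15C and 5% on placebo. With 305 per arm, 305 × 0.14 = 42.7 and 305 × 0.05 = 15.25, so about 43 versus 15 subjects.

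**3. Effect on the AE analysis.** Simulation: 1,500 trials, 305 per arm, uniform accrual over 36 months, cut at month 48, true hazard ratio 0.62, AE stops spread over the first 16 weeks and independent of worsening, unstratified. Nominal significance is at two-sided 0.044. The primary analysis gives 0.62.

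| AE stoppers who stay and are not coded as AE drop-outs | HR | Nominally significant | Events, UT-15C vs placebo |
|---|---|---|---|
| 0% (same as keying to drug stop) | 0.84 | 27% | 128 vs 150 |
| 25% | 0.79 | 45% | 118 vs 146 |
| 50% | 0.74 | 65% | 107 vs 142 |
| 75% | 0.68 | 82% | 97 vs 139 |
| 100% (repeats the primary) | 0.62 | 93% | 87 vs 135 |

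The crude event ratios move the same way: 128/150 = 0.85, 107/142 = 0.75, 87/135 = 0.64. If stayers are counted but dated at Week 24, the HR stays at about 0.84. Who is counted matters; the date hardly does.

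**4. Dependence on the assumed AE rate.** Second simulation: 610 subjects, cut at 205 events, 70% of AE stops before Week 24 (only these can be missed), 600 runs.

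| AE stops, UT-15C vs placebo | HR keyed to drug stop | HR if 30% / 50% / 80% of early stoppers are missed |
|---|---|---|
| 14% vs 5% | 0.82 | 0.78 / 0.75 / 0.70 |
| 10% vs 5% | 0.75 | 0.72 / 0.70 / 0.67 |
| 7% vs 5% | 0.69 | 0.67 / 0.66 / 0.65 |

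Keyed to drug stop, the mean z is −2.2 at 10% versus 5% and −2.8 at 7% versus 5%, so at those rates the reading changes little either way.

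**5. All-cause analysis.** With 22% versus 14% stopping (TDE-PH-301, about 67 versus 43 subjects), the HR is 0.87 keyed to drug stop, and 0.87 to 0.88 if stayers are counted but dated at Week 24.

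**The case against.** **The terms may be interchangeable.** SAP 8.3.1 censors early study drop-outs at their last assessment before down-titration or drug stop, and early termination there and in the SAP 16.1 table titles could mean drug termination. Protocol 6.2 and 7.5 state one open-label entry rule, once in terms of drug and once in terms of study. That reading would close the gap. It is possible, but the operational text in SAP 10.1.1.3 says study, and SAP 9.1 keeps the two apart, so the programmer would have to choose.

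**The miscoding is not certain.** No section lists completion of Week 24 as an exit reason, and an AE stopper's exit could be coded as AE. Staying is encouraged, not required, and only for stops before Week 24. A reader might infer that the protocol holds all these subjects in the study; it does not. The supported word is can.

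**Both analyses do not fail alike.** A reader might infer that the all-cause check also misses these subjects, which would move its HR from 0.87 towards 0.62. The documents do not support that. Under Protocol 3.1 a subject continues until worsening, about 205 events or premature discontinuation, so one who leaves after Week 24 with neither of the first two has most likely dropped out early and is counted. The less favourable all-cause result would thus still be reported.

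**The 14% versus 5% may not carry over.** TDE-PH-301 was a twice-daily study begun at 1 mg with 1 mg steps. Protocol 1.2.4 reports no AE discontinuations among 23 subjects with 0.25 mg tablets at randomization, and this trial starts at 0.125 mg three times daily. This stands, and is why a range is shown.

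**Conclusion.** The point holds for the AE sensitivity analysis. As written, it can leave censored the subjects whose censoring it should test, and no section says how they are classed or dated. For the all-cause analysis the fault is an ambiguous or late date, with negligible numerical effect.

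The size is unknown, because the AE stop rate, the share who stay and their exit coding are not given. It runs from a change in how the check reads (0.84 against 0.62 to 0.79 at 14% versus 5%) to 0.02 to 0.04 on the HR at 7% versus 5%. The figures assume that AE stops are independent of worsening and that every missed stayer has a non-AE exit reason. It would go too far to infer that the plan will wrongly confirm its primary result. The primary test, alpha, 205 events and sample size are unaffected. The change should be made because the check is meant to support the primary result and the correction is cheap.

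**What to change.** Before unblinding, replace the definitions in SAP 8.3.1 and 10.1.1.3 with text such as:

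> Subjects who permanently discontinue study drug prematurely, that is, before study closure and for a reason other than clinical worsening, and who have no adjudicated event in the primary analysis, are counted as events on the date at which the primary analysis censors them, whether or not they remain in the study to Week 24. The second analysis is restricted to those whose recorded reason for stopping study drug is an AE. Subjects whose drug stops only because about 205 events have accrued or the study is closed remain censored.

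The last sentence is needed because ongoing subjects also have a Study Drug Termination Visit at closure (Protocol 7.4) and must not become events.

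Three points go with it:
- State how subjects whose investigator-reported event was rejected by adjudication are handled.
- Name one primary censoring date. SAP 8.3.1 uses last dose, last assessment, or last assessment before down-titration or drug stop; SAP 8.5 uses last assessment; SAP 10.1.1.2 uses drug discontinuation. For a stayer these can differ by weeks.
- Reconcile Protocol 4.3.1. For a second oral therapy begun before Week 24, one statement stops drug and encourages staying, while another takes the subject out of the study.

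Cost: short edits in SAP 8.3.1, 8.5, 10.1.1.2 and 10.1.1.3, plus the protocol clarification. No new data are needed, since the drug-stop reason and last dose date are already recorded. The downside is that the sensitivity result may look less favourable to UT-15C.

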1.2.4 Efficacy and Safety Data

UT-15C has previously been evaluated in three randomized, placebo-controlled Phase 3 studies (TDE-PH-301, TDE-PH-302, and TDE-PH-308). Additionally, subjects completing these studies have been provided long-term access to UT-15C in an open-label extension study (TDE-PH-304). To date, over 1000 PAH patients have been exposed to study drug (UT-15C or placebo) in the TDE-PH-301, TDE-PH-302, and TDE-PH-308 studies and over 890 patients have received UT-15C in the open-label extension study.

TDE-PH-301 was a 16-week, randomized, double-blind, placebo-controlled, international Phase 3 efficacy and safety study of treprostinil diethanolamine (UT-15C), in patients with PAH. Patients received UT-15C or placebo BID in combination with an ERA, a PDE5-I, or both. The primary endpoint was placebo-corrected change in 6MWD from Baseline to Week 16. Secondary endpoints included Borg dyspnea score, dyspnea-fatigue index, WHO Functional Class, and time to clinical worsening. Study drug dose was titrated up to a maximum of 16 mg BID based on clinical response and study drug tolerability.

Three-hundred fifty-four subjects were enrolled with 30% receiving an ERA alone, 25% a PDE5-I alone, and 45% both agents. The population was 81% female, predominantly WHO Functional Class III (76%), and had a mean baseline 6MWD of 346 m. PAH etiology included idiopathic or heritable PAH (66%), or PAH associated with CTD (26%), repaired congenital systemic-to-pulmonary shunt (7%), or HIV infection (1%). There were no remarkable demographic differences between treatment groups.

Twenty-two percent of subjects discontinued UT-15C therapy compared to 14% in the placebo group. The primary reason for discontinuation was AEs: 14% in the UT-15C group compared to 5% in placebo. There were three deaths in each of the treatment groups.

The Hodges-Lehmann (H-L) estimate of 6MWD placebo corrected median change from baseline at Week 16 was +11 m ($p=0.072$). The change in 6MWD was significant at Week 12 (+13 m, $p=0.015$). The lack of significance at Week 16 may be attributable to the number of subjects who did not provide an efficacy measure at Week 16 due to discontinuing from the study prematurely.

Secondary endpoints of the combined 6MWD and Borg dyspnea score and the dyspnea-fatigue index demonstrated statistically significant changes at Week 16 for UT-15C compared to Baseline ($p=0.013$ and 0.01 , respectively).

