### 5 SAMPLE SIZE CONSIDERATIONS

Approximately 205 adjudicated clinical worsening events will provide at least 90% power with a type I error rate of 0.05 (2-sided hypothesis) to detect a difference in the time to clinical worsening between treatment groups, assuming exponential distributions and an underlying hazard ratio of 0.62. Assuming a placebo median event time of 32 months (which corresponds to an event rate of 23% at Month 12), this hazard ratio corresponds to a median time to event of 51 months for the UT-15C group (which corresponds to an event rate of 15% at Month 12). Further assuming subject accrual is completed during the first 3 years with a 10% dropout rate at the end of the study, a total sample size of at least 610 subjects with a maximum of 850 subjects is expected to generate approximately 205 adjudicated clinical worsening events over the course of the study.

The primary efficacy endpoint of time to adjudicated clinical worsening events will be tested at an interim analysis when 75% of total adjudicated clinical worsening events have occurred with an alpha level of 0.020, and at the final analysis at an alpha of 0.044 with the overall Type I error rate at 0.05. Efficacy boundaries for early stopping of the study for efficacy are calculated based on O'Brien-Fleming alpha-spending function.

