#### 8.3.1 *Missing Data Handling for Time to Clinical Worsening*

For the analysis of time to clinical worsening, subjects who do not have an adjudicated clinical worsening event will be censored at the time of their last known study drug dose. For subjects who are reported as having a clinical worsening event by the Investigator and subsequently are classified as not having a clinical worsening event by the adjudication committee, the time to clinical worsening is also censored at the time of their last assessment date. For subjects who dropped out of the study early without experiencing a clinical

worsening event, the subjects will be censored at the time of their last assessment prior to down-titration or discontinuation of study drug.

In addition, the following 2 additional analyses will be performed on the primary efficacy endpoint (adjudicated time to clinical worsening) to assess the impact of missing data:

1. Early termination treated as clinical worsening event
2. Early termination due to AEs treated as clinical worsening events

For the mortality analysis, the vital status (live/dead status) for all subjects will be collected throughout the study to the study closure (the last patient last visit). Vital status for subjects who discontinued the study early is included in this mortality analysis. If the vital status is unknown at study closure, the time to death will be censored at the last known date the subject is alive.

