##### 10.1.1.1 *Hypothesis*

The study is designed to determine the efficacy of UT-15C compared with placebo in subjects with PAH. The null hypothesis tested for the primary endpoint of time to adjudicated clinical worsening is that there is no difference in hazard ratio in the time to clinical worsening of PAH when treated with UT-15C compared with placebo:

$$H_0: \text{hazard ratio} = 1$$

The 2-sided alternative hypothesis is that there is a difference:

$$H_a: \text{hazard ratio} \neq 1$$

Due to the alpha spending on interim analysis, for the final analysis, the significance level for the primary efficacy analysis of time to adjudicated clinical worsening is 0.044.

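### The only missing-data checks on non-fatal worsening score early drop-outs as worsening events in both arms, so any excess of discontinuation on UT-15C biases them against the drug and a failed check cannot be interpreted

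*SAP*

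**What the plan says.** The primary null in SAP 10.1.1.1 concerns worsening alone: "there is no difference in hazard ratio in the time to clinical worsening of PAH when treated with UT-15C compared with placebo". The primary analysis (SAP 10.1.1.2) censors subjects who stop study drug for reasons other than clinical worsening.

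SAP 8.3.1 then adds two analyses of the primary endpoint ("adjudicated time to clinical worsening) to assess the impact of missing data"). In the first, early termination counts as a worsening event. In the second, only early termination due to AEs does. SAP 10.1.1.3 repeats both for all subjects, without distinction by arm, and times the event at discontinuation. For the second it says: "For all subjects who drop out from the study early due to AEs, they are considered as having a clinical worsening event". The results go to Tables 14.2.1.3 and 14.2.1.4.

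Other planned analyses vary the population (per-protocol), the event source (investigator-reported) or the event date (first rather than confirmatory walk test, SAP 8.5). Vital status is collected to study closure (SAP 8.3.1 and 10.1.1.3; Protocol Appendix 15.7), but this informs death only. No planned analysis varies the assumed risk of non-fatal worsening after drop-out.

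**The concern.** The difficulty is the value assigned to a drop-out. The plan expects 23% of placebo subjects to worsen by Month 12. The checks give a drop-out a certain event on the day of leaving. They do so in both arms, so their null is no difference in worsening or discontinuation. That null is false whenever UT-15C is less well tolerated, whatever the drug does to worsening.

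The only gap the documents quantify is from TDE-PH-301 (Protocol 1.2.4): "The primary reason for discontinuation was AEs: 14% in the UT-15C group compared to 5% in placebo". All-cause discontinuation there was 22% vs 14%. If a gap of that kind recurs, a sound primary result may fail its own robustness check because of prostacyclin side effects. Nobody could then tell that from a result undermined by informative censoring, which is the question SAP 8.3.1 sets out to answer.

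**Working it through.** **Inputs from the documents.** SAP 5: "Approximately 205 adjudicated clinical worsening events will provide at least 90% power with a type I error rate of 0.05 (2-sided hypothesis". The same section sets a hazard ratio of 0.62 under exponential worsening, and a placebo median of 32 months, or 23% with an event by Month 12. SAP 10.1.1.1: "the significance level for the primary efficacy analysis of time to adjudicated clinical worsening is 0.044". Also 610 to 850 subjects randomised 1:1, accrual over 3 years, and 10% drop-out with no split by arm.

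**1. Reproduce the plan's figure.** Power = Φ(√(d/4)·|ln HR| − z). With d = 205 and HR = 0.62, √51.25 × 0.478 = 3.422.
- At 0.05: Φ(3.422 − 1.960) = 92.8%.
- At 0.044: Φ(3.422 − 2.014) = 92.0%.

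At least 90% is confirmed. The Month 12 placebo rate, 1 − 2^(−12/32) = 22.9%, also agrees with the plan.

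**2. Simulate the AE check.** Worsening is exponential (placebo median 32 months), accrual uniform over 36 months, cut-off at the 205th event, log-rank at two-sided 0.044 (2.2% per side), N = 610. Assumptions not in the documents are these: drop-out is independent of worsening, study-drug discontinuation is treated as study drop-out, the test is unstratified, and there is no interim look. Ranges span repeated runs.

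| AE drop-out, UT-15C vs placebo | Timing | Rejection at HR 1 | Power at HR 0.62 |
|---|---|---|---|
| 14% vs 5% | first 16 weeks | 37-39% | 22-24% |
| 14% vs 5% | over 24 months | 16-20% | about 40% |
| 7.8% vs 2.8% | first 16 weeks | 14-15% | 53-56% |
| 7% vs 2.5% | over 24 months | 7-8% | 68-74% |
| 5% vs 5% | first 16 weeks | about 2% per side | about 88% |

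Wherever there is a gap, the rejections at HR 1 are almost all against UT-15C. At the full early gap, rejection in its favour is 0.1% or less. The primary analysis keeps 91-92% power and about 2% per side throughout.

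The third row scales TDE-PH-301 to the plan's drop-out. Its pooled rate is (22 + 14)/2 = 18%, and 10/18 = 0.556, so 14% × 0.556 = 7.8% and 5% × 0.556 = 2.8%.

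**3. Check by hand.** At the full early gap, about 41 UT-15C and 15 placebo drop-outs join the 205 events, giving 261.
- At true HR 1 the average estimate becomes 1.23: √(261/4) × ln 1.23 = 1.672, and Φ(1.672 − 2.014) = 37%.
- At true HR 0.62 it becomes 0.86: √(261/4) × |ln 0.86| = 1.218, and Φ(1.218 − 2.014) = 21%.

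Both are close to the simulation.

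**4. Other settings.** The all-drop-out check behaves alike. At N = 610 it gives 33% and 23% with the full gap, and 13% and 54% with the scaled gap. At N = 850 the AE check gives 52% and 9% (full gap), and 19% and 42% (scaled gap).

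**5. The alternative analysis.** Imputing UT-15C drop-outs at the placebo hazard times delta was run at N = 610 with the full early gap. At delta 1 it rejects about 2.4% of the time at HR 1 and has 86-87% power at HR 0.62. Power is 69-71% at delta 1.5 and 56% at delta 2. The decline is gradual, which is what makes a tipping point informative.

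**The case against.** Several points on the other side stand.

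- **The gap is not known for this trial.** TDE-PH-301 was dosed twice daily and began with a 1 mg starting dose and 1 mg increments. This trial is dosed three times daily from 0.125 mg. Protocol 1.2.4 reports 0% AE discontinuation in 23 subjects with 0.25 mg tablets at randomisation, and a low but unquantified rate in TDE-PH-302. Protocol 1.4 hypothesises fewer prostacyclin AEs with the new regimen.
- **A reader might infer that the checks lose most of their power.** That needs roughly the full earlier gap. With half rates over 24 months, about 70% power remains.
- **A reader might infer that the checks measure tolerability.** They measure worsening and discontinuation together.
- **A reader might infer inflated Type I error.** The checks lie outside the alpha-controlled tests in SAP 8.4, and the bias shown runs against UT-15C.
- **The simulation inputs are approximate.** TDE-PH-301 reports stopping therapy, whereas the checks concern leaving the study, and Protocol 7.4 encourages early stoppers to stay to Week 24. Protocol 4.3.1 also takes subjects given a second oral PAH therapy off study drug or out of the study, including for progression short of the endpoint. If the drug works, these would be commoner on placebo, and under the all-drop-out rule they would offset some of the loss. This was not modelled.

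It can also be said that a conservative stress test is legitimate, and that a primary result which survives an excess of UT-15C drop-outs scored as events is credible. That is fair, so it would go too far to say the trial cannot learn whether its result survives missing data. But the scheme fixes one extreme value in both arms and offers no gradation, so failure remains uninterpretable.

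**Conclusion.** The concern holds in limited form. As the missing-data assessment for non-fatal worsening, the two checks answer a different question from the one stated. Any excess of discontinuation on UT-15C biases them against the drug.

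The size is conditional on the gap. At N = 610, rejection against UT-15C at hazard ratio 1 runs from about 2% with no gap to 37-39% with the full early gap, and power at 0.62 runs from about 88% down to about 23%. At the plan's own 10% drop-out the figures are about 15% and 53%. All of this rests on the assumptions in the working, above all independence of drop-out from worsening and the equating of stopping drug with leaving the study.

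The documents do not support treating the earlier gap as a fact about this trial, or reading this as a threat to the primary test. It is a worthwhile, inexpensive improvement to a supportive analysis.

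**What to change.** Add to SAP 8.3.1 and 10.1.1.3 a reference-based, delta-adjusted multiple imputation of the primary endpoint:

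1. For UT-15C drop-outs, draw event times after drop-out from the placebo hazard in their randomisation stratum, multiplied by delta = 1, 1.5, 2 and upwards.
2. For placebo drop-outs, draw from the placebo hazard.
3. Censor at the study cut-off and run the stratified log-rank test on each imputed set.
4. Pool by Rubin's rules and report the delta at which significance is lost.

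Keep Tables 14.2.1.3 and 14.2.1.4 as supportive analyses, retitled as clinical worsening or discontinuation, and do not present them as the missing-data check.

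The cost is SAP wording, one program and one table, with no new data, visits or subjects. The downside is that the tipping delta needs clinical interpretation.
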